4.9. Case management

From screening to discharge, patients' safety will be ensured through following procedures, which are also indicated in **Table 4: schedule of activities**. Screening procedures will be started only after obtaining written informed consent. During screening, medical and medication history will be collected and patients' condition will be monitored through physical examination, obtaining vital signs, assessment of stool and urine output vomiting, dehydration status, water intake, ORS intake and IV fluid infused, and testing for complete blood count (CBC) and serum electrolytes and creatinine. For female of child bearing age pregnancy will also be evaluated as a part of the exclusion criteria. All the inclusion and exclusion criteria will be strictly maintained for enrollment of the patients in the study, and no vulnerable participants will be enrolled. After randomization and administration

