5.0 Sample Size Calculation and Outcome (Primary and Secondary) Variable(s)

Clearly mention your assumptions. List the power and precision desired. Describe the optimal conditions to attain the sample size. Justify the sample size that is deemed sufficient to achieve the specific aims.

Planned screening is 500 participants. ITT (intention to treat) group is 150 patients. Enrollment will stop once 150 participants are recruited, or once 100% of per-protocol dataset (PP) is achieved. Sample size was calculated based on the mean volume of stool output in cholera patients. Mean stool output was assumed at 280 ± 156 g/kg²²⁻²⁴. Assuming 33% reduction (alternative hypothesis) vs no reduction (null hypothesis), sample size was calculated using GraphPad Prism software for two-tailed t-test with alpha 5% and power 0.8. Using recruitment of 50 participants per arm (100 total), power level of 0.82 can be achieved. Although, this is a sufficient level of power for the projected study, data points lost due to participant drop-out, cross-over to other study arms, withdrawal and missing data will affect the power of the study. We calculated that recruitment of up to 75 patients per study arm would allow power of 0.94.

Endpoints associated with primary and secondary objectives, and justification for endpoints are given below (Table 1).

Table 1-Primary and Secondary Objectives and Endpoints

OBJECTIVES	ENDPOINTS	JUSTIFICATION FOR ENDPOINTS
Primary		

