6.0 Data Analysis

Describe plans for data analysis, including stratification by sex, gender and diversity. Indicate whether data will be analysed by the investigators themselves or by other professionals. Specify what statistical software packages will be used and if the study is blinded, when the code will be opened. For clinical trials, indicate if interim data analysis will be required to determine further course of the study.

Data analysis must comply with ICH E9 Guideline and ICH E9(R1) Guideline. All relevant data collected in the trial should be considered in the statistical considerations section.

The analysis will be conducted on all participant data at the time the trial ends.

Statistics for primary end-point data and parametric secondary end-point data will be presented via means (alternatively, LSMEANS) with standard deviations; primarily two-tailed Student's t-test will be used for analysis with significance level of $p \leq 0.05$. For non-parametric analysis, such as lifetime data, Kaplan-Meier analysis will be used with significance level of $p \leq 0.05$. Some data might be expressed and analyzed as % values, such as the occurrence of unscheduled IV rehydration.

Analysis of secondary endpoints will be performed through the same method of the primary endpoint, which is found via a one- sided two sample unequal variance Student's t-test. The scale for each secondary endpoint will be nominal and will be determined at a single endpoint, which is at the end of intervention. The results will be presented by LSMEANS (Least-squares Means) with standard errors.

Primary Endpoint:

Reduction in stool output volume (ml/hour) over a treatment period measured and plotted as total stool output during 12-hour stool collection at every 12 hours for 72 hours.

Secondary Endpoints:

- Time until the stool volume output of 200mL/hour or less. Duration of stool output in excess of 200mL/hour per patient will be recorded between the start and end of the treatment for both treatment groups.
- Time until recovery. Duration of diarrhea until the passage of first non-watery stool or no stool for 12 hours or the end of treatment (72 hours) will be derived from date and time records in daily stool charts.

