6.2. Analysis Supporting Primary Objectives

6.2.1. Statistical Model, Hypothesis, and Method of Analysis

Primary Endpoint:

Reduction in stool output volume over a treatment period.

Primary Endpoint 1., Hypothesis 1. Treatment with VR-AD-1005 reduces stool output in patients with diarrhea due to *V. cholerae* infection. Null hypothesis is stated as no statistically significant difference in stool output volume as compared to placebo; alternative Hypothesis 1 is stated as statistically significant reduction in stool output volume in patients treated with VR-AD- 1005.

Two analytical approaches are proposed. Approach 1 will be based on the total quantity of stool purged by participant during the intervention administration period. Stool output will be expressed as g/kg body weight based on the stool charts, and the means will be compared between intervention and placebo groups using Student's unpaired t-test. In approach 2, stool purging is measured and plotted as total stool output in ml/kg/12 hours based on the individual stool collection charts. Weight of stool will be converted to volume using 1:1 weight/volume ratio. Diarrhea of cholera resolves rapidly, and majority of patients are expected to recover within 30-50 hours after randomization. 12-hour analysis increments allow a better insight into the onset and timing of the effect of study intervention as compared to cumulative data over the duration of the treatment. Means will be compared for each 12-hour period after first intervention administration using unpaired Student's t-test. Normal distribution is assumed for both cases. Analysis will be conducted in the ITT, MITT and PP groups. Missing data and outliers will be handled using imputation technique. Non-adherence and lost to follow-up patients will be categorized into the appropriate group and handled accordingly. No subtractions will be made from the ITT group after randomization assignment.

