Appendix I

Schedule of activities

Procedures	Screening Hour - 4	Day1 Hour 0:00	Day 1 Time +5:00 hr	Day 1 Time+1 0:00 hr	Day 1 Ho_Time +15:00 hr	Day 2 Hour 0:00	Day 2 Time +5:00 hr	Day 2 Time +10:00 hr	Day 2 Time +15:00 hr	Day 3 Hour 0:00	Day 3 Time +5:00 hr	Day 3 Time +10:00 hr	Day 3 Time +15:00 hr	End of treatment
Informed consent	X													
Demographics	X													
Medical history	X													
Pregnancy screening	X													
Randomization and dispensation of numbered IP	X													
Concomitant medication review	X	X				X				X				
Physical exam (including Height and weight)	X	X				X				X				X
Vital signs BP, pulse, temperature	X	X				X				X				X
Blood collection for CBC	X	X				X				X				X
Blood collection for BMP	X					X								X
Assessment of stool output	X	X	X	X	X	X	X	X	X	X	X	X	X	X
Assessment of vomiting	X	X	X	X	X	X	X	X	X	X	X	X	X	X
Assessment of rehydration	X	X	X	X	X	X	X	X	X	X	X	X	X	X
Assessment of dehydration	X	X	X	X	X	X	X	X	X	X	X	X	X	X
Assessment of IV fluid infused	X	X	X	X	X	X	X	X	X	X	X	X	X	X
Assessment of water intake	X	X	X	X	X	X	X	X	X	X	X	X	X	X
Assessment of ORS intake	X	X	X	X	X	X	X	X	X	X	X	X	X	X
Assessment of urine output	X	X	X	X	X	X	X	X	X	X	X	X	X	X

Collection of stool samples for V. Cholerae confirmation	X													X
Stool collection for electrolytes	X					X								X
Administer study intervention		X	X	X	X	X	X	X	X	X	X	X	X	
Initiate rehydration and/or antibiotics treatment		X	X	X	X	X	X	X	X	X	X	X	X	
Adverse Events		X	X	X	X	X	X	X	X	X	X	X	X	X
Complete Case Report Forms (CRFs)	X	X	X	X	X	X	X	X	X	X	X	X	X	X

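### The primary comparison is an unadjusted t-test although stool output is scheduled for assessment before the first dose: a missed gain in precision, not an error

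*Combined protocol and SAP*

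**What the plan says.** Section 6.2.1 sets out two approaches to the primary endpoint. For total output in g/kg, "the means will be compared between intervention and placebo groups using" an unpaired Student's t-test. For output by interval, "Means will be compared for each 12-hour period after first intervention administration using unpaired Student's t-test". Neither names a covariate, and scaling to body weight is the only adjustment.

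Section 6.0 says that results will be "presented via means (alternatively, LSMEANS) with standard deviations". Least-squares means need a fitted model, and none is given. ANCOVA appears in the list of abbreviations but in no analysis section.

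Stool output is on the schedule before dosing. Section 4.9 includes in screening the "assessment of stool and urine output vomiting, dehydration status, water intake, ORS intake and IV fluid infused". In Appendix I the row "Assessment of stool output" is marked at Screening (Hour -4), and study drug is first given at Day 1 Hour 0:00.

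The documents do not say how that pre-dose assessment is made. Section 4.5.1 lists baseline stool only for the rapid test and culture. Section 4.5.2 starts the weighed efficacy collection after the first dose. No weighing, time window or unit is stated for the screening value.

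Sections 4.4.6.2 and 4.4.6.3 describe block randomisation and mention no stratification. Section 6.5 adds that the severity subgroups do not affect randomisation.

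**The concern.** How fast a patient is purging before treatment is a natural candidate predictor of how much that patient purges afterwards. If it does predict, an analysis that ignores it leaves explainable variation in the error term, and a chance difference between arms in initial purging passes into the estimated effect. Section 4.1 recognises that baseline differences can distort the comparison but plans only to describe them. With neither stratification by severity nor adjustment, nothing in the design or the analysis deals with such a difference.

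At stake are the width of the confidence interval and some protection of power if analysable numbers fall. Section 5.0 expects losses from drop-out, withdrawal and missing data, and section 4.3 takes culture-negative patients out of the final analysis. There is also the open reference to LSMEANS: a covariate chosen after unblinding could be challenged, whereas one named in advance could not.

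**Working it through.** **Inputs.** Section 5.0 gives the planning figures: "Mean stool output was assumed at 280 ± 156 g/kg" and "Assuming 33% reduction (alternative hypothesis) vs no reduction (null hypothesis". It also gives a two-tailed t-test at 5%, and stated power of 0.82 at 50 per arm and 0.94 at 75 per arm. The correlation r between pre-dose rate and total output is not in the documents. It is an assumption here, shown from 0 to 0.7.

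**Step 1: reproduce the plan's power.** Difference = 0.33 × 280 = 92.4 g/kg; standardised, 92.4 / 156 = 0.592. The standard error is 156 × √(2/n), which is 31.2 at n = 50 and 25.47 at n = 75. The noncentrality is 92.4 / 31.2 = 2.96 and 92.4 / 25.47 = 3.63. The noncentral t distribution, two-sided 0.05, gives power 0.835 and 0.950, within two points of the stated 0.82 and 0.94. One-sided versions give 0.903 and 0.975 and do not match. The planned power is therefore that of an unadjusted two-sided test, with no credit taken for a covariate.

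**Step 2: effect of adjustment.** With one baseline covariate the residual SD is 156 × √(1 − r²), so variance falls by r², and the error degrees of freedom drop by one. The equivalent unadjusted size is 75 / (1 − r²).

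| r (assumed) | Variance reduction | Power, 50 per arm | Power, 75 per arm | 95% CI half-width, 75 per arm (g/kg) | 75 per arm is worth (per arm) |
|---|---|---|---|---|---|
| unadjusted | – | 0.835 | 0.950 | 50.3 | 75 |
| 0.1 | 1% | 0.838 | 0.952 | 50.1 | 76 |
| 0.2 | 4% | 0.849 | 0.957 | 49.3 | 78 |
| 0.3 | 9% | 0.867 | 0.965 | 48.0 | 82 |
| 0.5 | 25% | 0.923 | 0.986 | 43.6 | 100 |
| 0.7 | 49% | 0.984 | 0.999 | 36.0 | 147 |

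**Step 3: cost if the covariate is useless.** At r = 0 the variance is inflated by about 1 + 1/(N − 4). With N = 150 that is 1.007, a loss under 1%. Break-even is at r ≈ √(1/(N − 3)) = √(1/147) ≈ 0.08.

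**Step 4: chance imbalance.** At 75 per arm, an imbalance of 1.96 standard errors in the pre-dose rate is 1.96 × √(2/75) = 0.32 SD. At r = 0.5 it moves the unadjusted difference by 0.5 × 0.32 × 156 ≈ 25 g/kg, or 27% of the 92.4 g/kg target. At r = 0.1 the shift is about 5 g/kg.

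**The case against.** The strongest reply is that a usable covariate has not been shown to exist. Weighed collection is specified only from the first dose. The four-hour window is no more than a column label: under section 4.9 screening procedures follow written consent, and under section 4.3 the first dose follows at once after consent and randomisation. Section 4.5.1 also has severely ill patients resuscitated before they can consent. The interval could be short and differ between patients, and a rate measured over it could be noisy. This stands. It means that the change is more than SAP wording, and a reader who infers that adjustment comes free goes further than the documents allow.

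Second, the predictive value is unknown. Section 6.3 itself notes that heavy early output may stop abruptly, and collection for the endpoint ends at recovery. Total output therefore depends partly on duration, which an initial rate may predict poorly. This also stands, and it is why the table includes weak correlations, where the gain is negligible.

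Third, a reader might take the planning SD of 156 on a mean of 280 as evidence that initial purging varies widely. It is not: those figures describe the stool output used for the sample size, and the documents give none for the initial rate.

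Fourth, the power needs no rescue. The unadjusted test has about 0.90 at 60 per arm and 0.835 at 50, still above the 0.80 target, and participants stay in hospital throughout treatment.

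These points narrow the case but do not remove it. Vessels, calibrated scales and stool charts are already in use, and an uninformative covariate costs under 1% of variance.

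**Conclusion.** The point holds as a cheap improvement. The primary analysis is unadjusted although stool output is scheduled for assessment before dosing, and an ANCOVA pre-specified on that measure would probably sharpen the estimate.

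It would be wrong to infer that the planned analysis is biased or invalid. Under randomisation the t-test keeps its type I error, chance imbalance included, and the stated power is reached without adjustment. At full enrolment the benefit is mainly a narrower interval: at r = 0.5 the half-width falls by 6.7 g/kg (50.3 − 43.6). Power gains matter more if analysable numbers fall towards 50 per arm, where the range is about 0.84 to 0.98 against 0.835.

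All of this rests on an assumed correlation of 0.1 to 0.7 and on a pre-dose rate that can be measured as a quantity. The existence of the scheduled assessment and the absence of any covariate are certain. The size of the gain is not, and it could be close to nil.

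**What to change.** 1. In the protocol, define the scheduled pre-dose stool output as a weighed amount with recorded start and stop times up to the first dose, expressed in ml/kg/h using the 1:1 weight-to-volume conversion already adopted. The timing of the first dose need not change.
2. In section 6.2.1, make the primary analysis an ANCOVA of total stool output (g/kg, from first dose to recovery or 72 hours, whichever is earlier, as Table 1 defines it) on treatment, with the pre-dose rate as covariate. Report the adjusted difference with its 95% CI. This also supplies the model that the reference to LSMEANS lacks.
3. Use the same covariate in the 12-hour comparisons.
4. State a rule for a missing baseline, for example mean imputation with a missingness indicator, because section 6.2.2 leaves planned baseline values out of its missing-data classification.
5. Keep the unadjusted t-test as a sensitivity analysis.

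The cost is one degree of freedom, a short protocol clarification with the matching SAP text, and timed weighing of pre-dose stool with equipment already in use. No extra visit or patient is needed.

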
 To assess the efficacy of VR-AD-1005 for the treatment of acute diarrhea in cholera patients in combination with standard treatment (rehydration and antibiotics, please see attached SoP for more details) versus standard treatment with placebo. Efficacy is measured as reduction in stool output between the start of treatment until final diarrheal stool before clinical recovery (defined as disappearance of watery stool and two consecutive passages of soft stool) or end of study treatment (treatment duration 72 hours), which is earlier. 	
 Reduction in stool output volume (ml/hour/kg) over a treatment period measured as stool weight and recalculated to stool volume using 1:1 w/v ratio, and plotted as stool output quantity per each 12-hour period for the duration stool collection. 6 points are expected for a 72-hour stool collection. Measurement of stool output will be performed by collecting the stool from a participant into the pre-weighed vessel. The vessel with stool will be weighed on the calibrated scale, the weight of the vessel would be subtracted, and the resulting stool weight recorded into the stool diary form. During weighing of stool, Infection Prevention and control (IPC) standards will be upheld by implementing protection of personnel via using appropriate personal protective equipment. Hand washing before and after stool weighing will be strictly adhered to thereby preventing infection of study personnel. After weighing, stool will be disposed of as biohazardous waste at study sites and the weighing vessel appropriately disinfected before next measurement or discarded, if disposable. 	
 Primary endpoint allows to monitor and characterize the efficacy of VR-AD-1005 for reduction of stool output. Over-secretion of hypotonic fluid occurs predominantly in the small intestine, and fluid is lost with stool. The volume of fluid loss in cholera patients can be life-threatening due to rapid dehydration. Thus, the primary efficacy endpoint is designed to demonstrate potential of VR-AD-1005 treatment to reduce fluid loss with stool.
Secondary		

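### The plan names no deciding test for the primary hypothesis, so its two-sided 5% alpha is not secured, and its stated power applies to only one of the competing analyses

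*Combined protocol and SAP*

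**What the plan says.** **Endpoint.** Table 1 (section 5.0) gives the primary endpoint as "Reduction in stool output volume (ml/hour/kg) over a treatment period measured as stool weight", plotted per 12-hour period, with six points expected over 72 hours. The objective beside it ends measurement at clinical recovery or at the end of the 72-hour treatment, whichever comes first. Section 6.0 gives "Reduction in stool output volume (ml/hour) over a treatment period measured and plotted", again by 12-hour collection but not divided by body weight.

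**Tests.** Section 6.2.1 states one primary hypothesis and then says "Two analytical approaches are proposed. Approach 1 will be based on the total quantity of stool purged by participant". That total, in g/kg, is compared by an unpaired t-test. Approach 2 uses ml/kg per 12 hours: "Means will be compared for each 12-hour period after first intervention administration". For both, "Analysis will be conducted in the ITT, MITT and PP groups".

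**Level and sidedness.** Section 6.0 sets significance at p ≤ 0.05 with a test that is primarily two-tailed. Its next paragraph, on the secondary endpoints, says they follow the primary endpoint's method and describes that method as one-sided with unequal variance.

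**Sample size.** Section 5.0: "Mean stool output was assumed at 280 ± 156 g/kg", a 33% reduction, and a "two-tailed t-test with alpha 5% and power 0.8". Power is stated as 0.82 with 50 per arm and 0.94 with 75 per arm.

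No section gives a testing order, a multiplicity adjustment or a rule for declaring success.

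**The concern.** A single hypothesis has several routes to a significant result, and the plan does not say which one counts. Someone following it exactly could find the total not significant and one 12-hour period significant, or ITT and PP in disagreement, and would have no pre-stated way to decide whether the trial met its primary objective.

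The sections also point in different directions. Both formal endpoint statements describe 12-hour quantities, which is Approach 2. The power calculation describes a total in g/kg, which is Approach 1. The power of 0.82 or 0.94 therefore says nothing about the analysis that the endpoint definitions suggest. The conflict over sidedness adds to this: for a single test, one-sided 0.05 allows twice the error in the drug's favour that two-sided 0.05 allows (0.05 against 0.025).

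**Working it through.** **1. Reproduce the stated power (total g/kg only).** Inputs from section 5.0: mean 280, SD 156, 33% reduction, two-sided 0.05.

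- Difference = 0.33 × 280 = 92.4 g/kg; standardised, 92.4/156 = 0.592.
- Standard error = 156 × √(2/n): 31.2 at n = 50 and 25.47 at n = 75 per arm.
- Noncentrality = 92.4/31.2 = 2.96 (98 df) and 92.4/25.47 = 3.63 (148 df).
- Power from the noncentral t: **0.835** at 50 per arm (stated 0.82) and **0.950** at 75 per arm (stated 0.94).

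Both are within two percentage points. A one-sided 0.05 test would give 0.903 and 0.975, so the stated figures fit a two-sided test of Approach 1.

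**2. Count the tests.** Approach 1 gives 1 and Approach 2 gives 6 (Table 1's six points), so 7 per population. With three populations, 7 × 3 = 21.

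**3. Count the measures.** With the plan's 1:1 weight-to-volume conversion, ml/hour/kg is ml/kg/12 h divided by 12, so the t-test gives the same p-value. Only ml/hour without division by weight is a different scale for the 12-hour data. The total in g/kg is a different quantity.

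**4. Error rate if any of the seven tests could carry the claim.** Independent tests would give 1 − 0.95⁷ = 0.302. The tests are not independent, because the periods come from the same patients and the total is their sum. I simulated six null period statistics and their weighted total (1,000,000 draws per setting; exchangeable or autoregressive correlation; equal or declining period weights), testing each at two-sided 0.05 in one population. The documents give no between-period correlation, so the whole range is an assumption.

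| Assumed correlation | Any p ≤ 0.05, either direction | Any p ≤ 0.05 favouring the drug |
|---|---|---|
| 0 | 0.28 | 0.15 |
| 0.3 | 0.25–0.26 | 0.12–0.14 |
| 0.5 | 0.21–0.24 | 0.11–0.12 |
| 0.7 | 0.16–0.20 | 0.08–0.10 |
| 0.9 | 0.11–0.13 | 0.05–0.07 |
| One designated test | 0.05 | 0.025 |

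All six periods are treated as analysable. Letting two further nested populations count as well (assumed to drop 8% and 16% of patients at random, equal period weights) gives 0.16 to 0.39 in either direction.

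**5. Compare remedies.** One designated test (Approach 1, one population, two-sided 0.05) keeps alpha at 0.05, with power 0.950 at 75 per arm and 0.835 at 50. Keeping all seven eligible under Bonferroni (0.05/7 = 0.0071) reduces power for the total to 0.814 and 0.586.

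**The case against.** The strongest reply is that the plan leans towards Approach 1 in ITT. The sample size uses total g/kg with a two-tailed test. Section 6.2.1 justifies the 12-hour periods as showing onset and timing, which is a descriptive purpose. ITT is the 150-patient set, is protected from subtractions, and is the set for which section 6.2.2 provides multiple imputation. If that reading is right, alpha is 5% and the stated power applies.

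This narrows the gap without closing it. None of these statements designates a deciding analysis, and Table 1 and section 6.0 define the endpoint in 12-hour terms. The population is unsettled too: section 4.3 leaves culture-negative recruits out of the final analysis, while section 6.2.1 allows no removal from ITT after randomisation. Nor does phase II status remove the problem, since the protocol sets a formal null hypothesis and a 5% alpha and commits to ICH E9.

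Three stronger readings are tempting, and the documents do not support them:

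- **That the trial's false-positive rate is several times 5%.** There is no success rule, so the rate is undefined. It is 5% if Approach 1 in one population decides, higher if any result suffices, and would be below 5% if every test had to succeed.
- **That the rate is 30% for seven tests, or 66% for 21 (1 − 0.95²¹).** Those figures need independent tests, and here both periods and populations overlap.
- **That every change of unit is a further chance of success.** The two per-kg rates are one measure rescaled.

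**Conclusion.** The concern holds as a specification gap that should be closed before unblinding. The plan does not secure its two-sided 5% alpha for the primary hypothesis, because it names no deciding approach, period, population or consistent sidedness. The stated power is essentially right, but for the total in g/kg only.

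The size is conditional. It assumes that any of the seven tests in one population may carry the claim, with each tested at two-sided 0.05. The chance of at least one false positive is then about 0.11 to 0.28 in either direction, or about 0.05 to 0.15 in the drug's favour against a reference of 0.025. The second pair is the relevant one for a claim of benefit. Both pairs rest on assumed correlations of 0.9 down to 0; the lack of a decision rule does not depend on them.

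**What to change.** In Table 1, section 6.0 and section 6.2.1:

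1. Name one primary endpoint and test: total stool output in g/kg (Approach 1, the quantity used for the sample size), unpaired t-test, two-sided 5%.
2. Keep the measurement period already in Table 1, from first dose to clinical recovery or 72 hours, whichever is earlier, and refer to it in section 6.2.1. A flat 72-hour total would be a different endpoint.
3. Name one deciding population. ITT fits section 6.2.1, but that section and section 4.3 must first be reconciled on culture-negative patients so that the set is defined.
4. Correct the one-sided, unequal-variance sentence in section 6.0 so that the primary test has one description.
5. Use one per-kg scale for the 12-hour data and drop un-normalised ml/hour from the primary endpoint.
6. Report the 12-hour comparisons as supportive estimates with confidence intervals, and the other populations as sensitivity analyses, with no success claim from either.

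The cost is wording, with no extra patients and no change to data collection. The sponsor gives up claiming primary success on a single 12-hour period or an alternative population. The designated test has power of about 0.95 at 75 per arm and 0.83 at 50 per arm under the plan's own assumptions.

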6.2.2. Handling of Missing Data

Missing data other than protocol-planned baseline values will be classified as missing completely at random (MCAR) or missing at random (MAR). MCAR can be confirmed by partitioning the data into two parts: one set containing the missing values, and the other containing the non-missing values. After partitioning the data, the t-test of mean difference is carried out in order to check whether there exists any difference in the sample between the two data sets. If the number of missing values is small, i.e. if the number of the cases is less than 5% of the sample, then the researcher can drop them. Otherwise, when analyzing using ITT population, model based multiple imputation (MI) will be used for both primary and secondary outcomes. The number of imputations will be the largest value of:

- 10, or
- The proportion of missing values for the actual variable * 100.

200 burn in iterations will be used for all analyses. Trace plots and distribution plots will be created to check the accuracy of imputations.

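### Undefined outliers are to be imputed, which discards observed stool outputs, lowers the SD and can bias the effect either way; the optional under-5% drop contradicts the ITT rule

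*Combined protocol and SAP*

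**What the plan says.** Section 6.2.1 (primary endpoint) states "Missing data and outliers will be handled using imputation technique", and section 6.3 repeats it for the secondary endpoints. Neither section defines an outlier, confines the rule to recording errors, says whether flagging is blinded, pooled or by arm, or plans an analysis with the observed values kept.

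Section 6.2.1 also says: "No subtractions will be made from the ITT group after randomization assignment".

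Section 6.2.2 deals with missing data only. It recognises two classes, MCAR and MAR. It says "MCAR can be confirmed by partitioning the data into two parts" and comparing these by t-test. It then allows that "if the number of the cases is less than 5% of the sample, then the researcher can drop them". Otherwise, model-based multiple imputation is used in the ITT population, with at least 10 imputations.

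Section 4.11 lets the investigator stop treatment or withdraw a patient for disease progression or adverse events. Section 6.5 plans a severe subgroup above 8 litres of stool per 24 hours.

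**The concern.** Stool is weighed on calibrated scales (sections 4.3 and 5.0, Table 1), so a very high value in severe cholera is more likely real than an error, and heavy fluid loss is what the drug is meant to reduce. Replacing such values removes outcome data and makes the rest look less variable than it is. Because the outlier rule is not stated, the primary p-value would depend on a choice made after the data exist.

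The drop option raises a second problem. It removes randomised patients from an analysis that is said to lose none. It is also discretionary, and it leans on a test that cannot establish what it is asked to. If patients leave because they are purging heavily, missingness depends on the outcome, and the plan has neither a class nor a sensitivity analysis for that.

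**Working it through.** **1. Inputs and the plan's own figure.** Section 5.0: "Mean stool output was assumed at 280 ± 156 g/kg", a 33% reduction, "two-tailed t-test with alpha 5% and power 0.8". The planned difference is 0.33 × 280 = 92.4 g/kg, so the treated mean is 187.6. Noncentral-t power with SD 156 in both arms is 0.835 at 50 per arm and 0.950 at 75 per arm. The plan gives 0.82 ("Using recruitment of 50 participants per arm (100 total), power level of 0.82 can be achieved") and 0.94, so its figures are reproduced to within 0.02.

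**2. Shape of the data.** Section 6.2.1 assumes normality. A normal curve with mean 280 and SD 156 puts Φ(−280/156) = Φ(−1.795) = 3.6% of patients below zero, which is impossible for stool weight, so right skew is plausible. Approach 2 is more exposed. Section 6.2.1 expects most patients to recover within 30–50 hours, so late 12-hour periods will hold many values near zero. If more than 75% of values in a period were exactly zero, both quartiles and the IQR would be zero, and a box-plot fence would flag every patient still purging.

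**3. Imputing outliers.** Assumptions, since the plan gives none: lognormal data, 75 per arm, values beyond 1.5 IQR of the quartiles flagged, each replaced by one draw from the unflagged values of the same arm, 4,000 simulated trials per case. The treated SD is either 156 (common) or 156 × 0.67 = 104.5 (proportional to the mean). Repeat runs differ by about 1 g/kg.

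| Flagging, treated SD | Flagged, placebo / treated | Difference (true 92.4) | Placebo SD (154 before) |
|---|---|---|---|
| Pooled, proportional | 5.5 / 1.0 | 68 | 105 |
| Pooled, common | 4.1 / 2.3 | 85 | 111 |
| Per arm, proportional | 3.1 / 3.1 | 86 | 117 |
| Per arm, common | 3.2 / 4.4 | 99 | 117 |

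With no true effect, type I error is about 0.06 pooled and 0.15 per arm, against about 0.05 with the values kept. Power can rise although the difference shrinks: in the pooled, common-SD case it goes from 0.93 to 0.99, because the SD falls by more than the difference.

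With the same fence in normal data, the difference is 85–87 pooled and 92–93 per arm, and the placebo SD falls only from about 155 to 143–151. A tighter rule matters even there: a pooled 2-SD cut-off in normal data with common SD gives 73.5 g/kg and power of 0.880 instead of 0.951.

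**4. Dropping missing cases.** 5% of 150 is 7.5, so at most 7 patients (4.7%) fall under the rule. The loss of numbers is minor: power is 0.940 with 71 and 72 patients instead of 0.950. Selection could matter more. If all 7 come from one arm and lie k SDs above its mean, the mean of the remaining 68 shifts by 7 × k × 156 / 68:
- k = 1: 16 g/kg, or 17% of 92.4.
- k = 2: 32 g/kg, or 35% of 92.4.

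Losses from placebo shrink the difference (to 60.3 at k = 2). Losses from the treated arm enlarge it by the same amount.

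**5. The MCAR test.** The t-test can only compare variables that are observed in both sets, so it says nothing about the missing values themselves. With 7 against 143 patients, its power to detect a 0.5 SD difference is 25%. A non-significant result is the likely outcome whether or not the data are MCAR.

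**The case against.** Four points on the other side deserve weight.

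- **Direction.** A reader might infer that the rule must shrink the effect because it removes mainly heavy purgers on placebo. The documents do not support that. The rule names neither arm nor high values. The fall to about 68 g/kg needs skewed data, pooled flagging and a treated SD that shrinks with the mean, whereas the plan's power figures fit a common SD. With per-arm flagging and a common SD, more treated than placebo values are flagged and the effect grows. This objection stands, and 68 is one end of a range.
- **Method.** The simulation used one draw per flagged value. The only method specified is multiple imputation, in section 6.2.2. If it also covers outliers, it would be expected to reduce the type I error inflation; this was not computed. But section 6.2.2 speaks only of missing data, and no form of imputation justifies replacing a valid measurement.
- **ITT.** A reader might take outlier imputation as a breach of ITT too. It is not: the patient stays in the analysis. Only dropping cases conflicts with the ITT rule, and that is optional and applies below 5%, not up to and including it.
- **Amount missing.** Patients remain inpatients for three days (4.3), stool is collected continuously during treatment (4.5.2), stool output is assessed when treatment is discontinued (4.11), and losses to follow-up come after treatment (4.12). These limit missing primary data, so seven losses from the upper tail of one arm is a worst case. Withdrawals during treatment remain possible.

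**Conclusion.** The point holds as a fault in the written rules, not merely a lack of detail: followed literally, they replace observed primary-endpoint values and permit removals that the same plan forbids. A lower SD was found under every rule tried, including 2-SD and 3-SD cut-offs and normal, gamma and lognormal data, though the fall is slight with a 3-SD rule in normal data. The direction and size of the bias in the effect are not determined by the plan. The range of about 68 to 99 g/kg around a true 92.4, and type I error of about 0.06 to 0.15, rest on lognormal data, a box-plot fence and single imputation. The 16–32 g/kg shift from dropping is a worst case. The conflict between 6.2.2 and the ITT rule, and the inability of a t-test to confirm MCAR, rest on no distributional assumption.

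**What to change.** - **Sections 6.2.1 and 6.3:** delete the reference to outliers from the imputation sentence. Keep every verified observed value. Correct only documented recording errors, identified while treatment is still blinded.
- **Sensitivity analysis 1:** prespecify a log-scale or rank-based analysis of stool output, to show how far the result depends on extreme values.
- **Section 6.2.2:** delete the option to drop cases below 5% and the t-test for MCAR. Use multiple imputation by arm for any amount of missing data in ITT.
- **Sensitivity analysis 2:** add a delta-shift analysis for patients who stop early, since section 4.11 allows stopping for reasons that may relate to stool output.

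The cost is SAP wording and two sensitivity analyses. No change to stool collection or other trial procedures is needed. The wording should be settled before unblinding.
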